## 16. EFFICACY OUTCOMES

Efficacy endpoints for PS will be analyzed at the end of each teduglutide treatment cycle (Week 24 or EOT), and at each study visit, relative to the baseline of the core study (TED -C13-003). The efficacy analyses will be performed on PS diary data and PS prescribed data for safety population. The descriptive statistics of efficacy outcomes will be summarized by treatment group as defined in Section 6. The listings for efficacy measures which are collected on the CRF forms will be provided.

### 16.1. EFFICACY ENDPOINTS

#### 16.1.1. EFFICACY VARIABLES & DERIVATIONS

The efficacy endpoints will be analyzed in two ways: 1) based on the subject diary data (also referred to as "actual"), and 2) based on the investigator-prescribed data (referred to as "prescribed"). PS will be reported in both subject diary data and the investigator-prescribed data in the eCRF. Investigator-prescribed data are the most recent PS prescription (prescription adjustments) prior to or on the date of visit, captured in the PS adjustments eCRFs. Data collected include prescribed weekly total kilocalories, volume, number of days per week, and average hours per day. PS diary data are collected 2 weeks prior to all scheduled site visits (except at pre-treatment visit) in the Intake Diary eCRFs over 24-hour periods that start on the assigned date. Depending on the time of day at which the 24 hour period begins, which can vary by subject, overnight PS volumes after midnight may be associated with prior the date. Data collected include actual PS total infusion duration, total volume and total kilocalories on the assigned date.

The calculation of average daily prescribed PS volume/caloric intake normalized to weight will follow the formula below:

Average daily value = (prescribed weekly PS parameter / 7) / last available weight prior to or on the date of visit.

The calculation of average daily actual PS will be based on the daily support recorded in

Document: \\quintiles.net\Enterprise\Apps\sasdata\SASa\sas\Shire\Teduglutide\ZXA48914\Biostatistics\Documentation\SAP\SHP633-303\_SAP\_Draft\_V1.0\_20171023

Author: [REDACTED] Version Number: Draft V1.2  
Version Date: 16Jan2018

Template No: CS\_TP\_BS016 – Revision 3  
Effective Date: 01May2012

Reference: CS\_WI\_BS005

Copyright © 2012 Quintiles Transnational Corp. All rights reserved.  
The contents of this document are confidential and proprietary to Quintiles Transnational Corp. Unauthorized use, disclosure or reproduction is strictly prohibited.

subjects' diaries within 7 days prior to the date of each scheduled visit. If more than 2 days' values in a week are missing, the average daily value will not be calculated and will be assigned as missing. The same strategy will be used to calculate all other average diary parameters. The calculation of actual PS volume normalized to weight will follow the formula below:

Average daily value = [(sum of non-missing actual daily values in the diary / number of days with non-missing values)] / last available body weight prior to the visit

Baseline actual PS will be calculated using all the diary data collected within 14 days prior to the first dose or baseline visit of the core study. If more than 5 days' values are missing in two weeks before the baseline visit the core study, the baseline values are missing.

#### 16.1.1.1. Reduction in PS volume

PS volume reduction at the end of each teduglutide treatment period (Week 24 or EOT) and at all other study scheduled visits compared to the baseline of the core study TED-C13-003 will be calculated using average daily values. The number and percentage of subjects who achieve at least a 20% reduction in PS volume (mg/kg/day) at the end of each teduglutide treatment period during the prospective observation period will be summarized. Similar analysis will be done for 50% and 75% reduction in PS volume. This parameter will be summarized for both actual and prescribed data.

#### 16.1.1.2. Change and percent change from baseline in PS volume and intake calories

Changes and percent change in prescribed and actual PS volume and intake calories from baseline to all the study visits are calculated following common calculations in Section 7.7. The baseline is defined as the PS data collected at the baseline of the core study TED-C13-003. These parameters will be summarized for both actual and prescribed data.

#### 16.1.1.3. Complete weaning off PS at EOT

A subject will be considered to have achieved independence from PS (completely weaned off PS) at the end of each teduglutide treatment period (Week 24 or EOT) if the investigator prescribes no PS at that visit and there is no use of PS recorded in the subject diary during the week prior to that visit.

The analysis will summarize how many subjects achieve complete weaning of PS at the end of each teduglutide treatment period (Week 24 or EOT).

---

Document: \\quintiles.net\Enterprise\Apps\sasdata\SASa\sas\Shire\Teduglutide\ZXA48914\Biostatistics\Documentation\SAP\SHP633-303\_SAP\_Draft\_V1.0\_20171023

Author: [REDACTED] Version Number: Draft V1.2  
Version Date: 16Jan2018

Template No: CS\_TP\_BS016 – Revision 3  
Effective Date: 01May2012

Reference: CS\_WI\_BS005

Copyright © 2012 Quintiles Transnational Corp. All rights reserved.  
The contents of this document are confidential and proprietary to Quintiles Transnational Corp. Unauthorized use, disclosure or reproduction is strictly prohibited.

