### **8.3. MISSING DATA**

Missing data will in general not be imputed. However, partial dates will contribute to the analysis as described in Appendix 2. All available data will be included in the safety analysis.

Details for the imputation algorithm for the missing endpoint values for PS parameters (volume, calories and etc.) will be described in Section [16.1.1](#) of this analysis plan.

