#### 16.1.1.4. Change and percent change from baseline in hours per day and days per week of PS

Change and percent change in hours per day and days per week of PS from baseline to each study visit will be summarized.

Hours per day of actual PS for all visits except the baseline visit will be calculated as follows:

Hours per day of actual PS = (sum of hours per day for each day that PS intake data is recorded within the 7 days prior to the visit / number of days that PS hours per day data is recorded within the 7 days prior to the visit)

Days per week of actual PS for all visits except the baseline visit will be calculated as follows:

Days per week of actual PS = (number of days with non-zero values for PS volume within the 7 days prior to the visit / number of days for which any PS intake data is recorded within the 7 days prior to the visit) \* 7

Prescribed PS hours per day and days per week for each visit (including baseline) will be taken from the most recent prescription data prior to or at that visit.

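### Complete weaning: with no PS prescribed, a blank or nearly blank diary week still meets the diary condition, so the diary does not always confirm independence

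*SAP*

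**What the plan says.** The prospective SAP defines complete weaning in Section 16.1.1.3 by two conditions that must both hold at the end of a teduglutide treatment period (Week 24 or EOT). The prescription condition is met "if the investigator prescribes no PS at that visit". The diary condition is met if "there is no use of PS recorded in the subject diary during the week prior to that visit". The section then promises a summary of how many subjects reach this status.

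Section 16.1.1 has a completeness rule for the pre-visit diary week: "If more than 2 days' values in a week are missing, the average daily value will not be calculated and will be assigned as missing". Its scope is then widened: "The same strategy will be used to calculate all other average diary parameters". Section 16.1.1.4 computes days per week of actual PS with this denominator: "number of days for which any PS intake data is recorded within the 7 days prior to the visit".

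On missing data, Section 8.3 says "Missing data will in general not be imputed" and sends the reader to Section 16.1.1 for missing PS endpoint values. Section 16.1.1 gives only the rule for diary averages and a separate one for the diary baseline. Nothing in Section 16 says how to classify weaning when diary days are missing.

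**The concern.** The diary condition is there to check the prescription against what the subject actually infused. It is worded as the absence of a recorded use. A record of zero use is not required, so seven days of recorded zeros and seven blank days both satisfy it.

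The prescription condition does not make the diary redundant. Under Section 16.1.1 the prescribed value is the latest prescription up to and including the visit date, so PS can be set to zero at the visit itself. In that case the diary is the only element of the definition that looks at use in the preceding week. If it is blank, a subject who infused PS during that week could still be counted as independent.

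The same subject-week could also be unusable for the actual-PS endpoints and yet a success on complete weaning. That sits badly in the clinical study report and invites two programmers to produce different counts.

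**Working it through.** The SAP gives no rate or figure for this endpoint, so there is nothing to reproduce. The check applies three rules as written to example diary weeks.

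**Rules**
- Weaned (16.1.1.3): prescription = 0, and no recorded day in the 7 before the visit has PS > 0.
- Average actual PS (16.1.1): sum of recorded values / number of recorded days; missing if more than 2 of 7 days are missing, so at least 7 − 2 = 5 recorded days are needed. The division by body weight is left out because it does not affect missingness.
- Days per week (16.1.1.4, formula read on its own): recorded days with PS > 0 / recorded days × 7.

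The last column applies the proposed definition. The volumes are invented for illustration.

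| Prescription | Diary week | Weaned as worded | Average actual PS | Days per week | With at least 5 of 7 days required |
|---|---|---|---|---|---|
| 0 | 7 zero | yes | 0 | 0/7 × 7 = 0 | confirmed |
| 0 | 5 zero, 2 missing | yes | 0 | 0/5 × 7 = 0 | confirmed |
| 0 | 4 zero, 3 missing | yes | missing | 0/4 × 7 = 0 | not evaluable |
| 0 | 1 zero, 6 missing | yes | missing | 0/1 × 7 = 0 | not evaluable |
| 0 | 7 missing | yes | missing | 0/0, undefined | not evaluable |
| 0 | 1 day of 300 mL, 6 zero | no | 300/7 = 42.9 mL | 1/7 × 7 = 1 | no |
| above 0 | 7 missing | no | missing | 0/0, undefined | no |

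**What this shows**
- Rows 3 to 5 are the problem. Weaning gets a definite yes while average actual PS is missing, and in row 5 days per week cannot be computed either.
- Rows 6 and 7 set the limits. A single recorded use defeats the status, and so does a non-zero prescription.
- For a fixed prescription, replacing a recorded day by a missing one can never turn 'weaned' into 'not weaned'. It can do the reverse if the lost day was a day of use. Within this condition the effect of missing days runs one way.

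The completeness rule does not repair this. Its text covers the average daily value and other averages, and weaning is a yes/no status.

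**The case against.** The best defence is that the SAP nowhere says in words that an empty diary means no use. The phrase can be read as a diary that was kept and shows none, and the statement in Section 8.3 that missing data are generally not imputed leans that way. Appendix 1 also provides a 'Missing' category for categorical tables, and actual and prescribed PS are summarized separately, so a shortfall of evaluable diaries would show in the number of subjects for actual PS. Efficacy is the secondary objective, and Sections 7.6 and 8.4 rule out significance claims and testing.

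Part of this stands. The blank-diary result follows from the literal wording and is not a stated convention. The setting is descriptive, which limits what is at stake. But the no-imputation statement and the 'Missing' category do not resolve the case, because the rule as written returns a definite status and leaves nothing to flag as missing. If the sponsor meant the stricter reading, the text still needs to say so.

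A second objection is that 5 of 7 days was chosen for averaging. PS can be prescribed on only some days of the week, so five zero days leave two unobserved. That is true: the threshold is a tolerance and does not prove zero use. Its merit is that weaning and actual PS would then be evaluable in the same weeks.

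A reader might also convert one subject into 1/40 = 2.5 percentage points. The documents do not support that. Forty is the expected total enrolment in Section 4.1, which includes subjects who consent only to retrospective data. Weaning is assessed only after a treatment period, Appendix 1 limits treatment-period tables to TED/TED, and Section 16.1.1.3 promises a count with no stated denominator.

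**Conclusion.** The point holds in a bounded form. As worded, Section 16.1.1.3 lets a subject with no PS prescribed at Week 24 or EOT meet the diary condition with a blank or largely blank week, provided no completed day shows use, although actual PS for that week is missing whenever more than 2 days are. In those cases the diary does not confirm independence, and missing days in this condition can only favour success.

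A reader might infer that an empty diary by itself makes a subject weaned, or that the reported count is known to be inflated. Neither follows. A zero prescription is still required, and a subject with no PS prescribed and a blank diary may be truly weaned. An error needs a zero prescription, missing diary days and actual use in that week together, and the SAP gives no frequency for any of these. The size is therefore unknown: each such subject changes the reported TED/TED count for the cycle by one.

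This assumes that the definition is programmed as written and that no diary instruction outside the SAP settles how blank days are treated. The change should be made, because the diary is the definition's only check on use in that week and the correction is inexpensive.

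**What to change.** In Section 16.1.1.3:

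1. Define 'diary-confirmed weaned' as no PS prescribed at the Week 24 or EOT visit, diary data on at least 5 of the 7 days before it (the tolerance already in Section 16.1.1), and zero PS on every recorded day.
2. Report subjects with no PS prescribed and fewer than 5 recorded days, none showing use, on a separate line: 'no PS prescribed, diary not evaluable'.
3. Name the denominator: subjects with a Week 24 or EOT visit in that cycle.

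The cost is a few sentences in a document still marked Draft V1.2, plus one table row; no new data are needed. The confirmed count may be lower, and some truly weaned subjects with sparse diaries will move to the separate line, where they remain visible.

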#### 16.1.1.4. Change and percent change from baseline in hours per day and days per week of PS

Change and percent change in hours per day and days per week of PS from baseline to each study visit will be summarized.

Hours per day of actual PS for all visits except the baseline visit will be calculated as follows:

Hours per day of actual PS = (sum of hours per day for each day that PS intake data is recorded within the 7 days prior to the visit / number of days that PS hours per day data is recorded within the 7 days prior to the visit)

Days per week of actual PS for all visits except the baseline visit will be calculated as follows:

Days per week of actual PS = (number of days with non-zero values for PS volume within the 7 days prior to the visit / number of days for which any PS intake data is recorded within the 7 days prior to the visit) \* 7

Prescribed PS hours per day and days per week for each visit (including baseline) will be taken from the most recent prescription data prior to or at that visit.

#### 16.1.1.5. Change in hours per day and days per week PN/IV Support from Baseline to End of Treatment within a cycle by Percent Reduction in PN/IV Volume

For  $\geq 20\%$ ,  $\geq 50\%$ , and  $\geq 75\%$  reduction in PS volume from Baseline to End of Treatment within a cycle, Change and percent change in hours per day and days per week of PS will be summarized.

### 16.1.2. ANALYSES OF EFFICACY VARIABLES

For the variables of pre-specified percent reduction in PS volume, the number and percentage of subjects will be presented by treatment group for treatment cycles and NTT periods. Baseline values, post-baseline values, change from baseline and percent change from the baseline in PS will be summarized by study visit and treatment group using descriptive statistics including number of subjects, mean, standard deviation, median, minimum and maximum.

---

Document: \\quintiles.net\Enterprise\Apps\sasdata\SASa\sas\Shire\Teduglutide\ZXA48914\Biostatistics\Documentation\SAP\SHP633-303\_SAP\_Draft\_V1.0\_20171023

Author: [REDACTED] Version Number: Draft V1.2  
Version Date: 16Jan2018

Template No: CS\_TP\_BS016 – Revision 3  
Effective Date: 01May2012

Reference: CS\_WI\_BS005

Copyright © 2012 Quintiles Transnational Corp. All rights reserved.  
The contents of this document are confidential and proprietary to Quintiles Transnational Corp. Unauthorized use, disclosure or reproduction is strictly prohibited.

## 17. HEALTH-RELATED QUALITY OF LIFE ANALYSIS

Health-Related Quality of Life Analysis is not applicable for the Interim Analysis.

Throughout the study, health-related quality of life (HRQoL) assessments will be performed using the Pediatric Quality of Life (PedsQL) Generic Core Scales at the time points CxD1, CxD12 and CxD24 for treatment period, at 12-week intervals for NTx and at EOS. The scales include self-reports for pediatric subjects and adolescents aged 5 to 18 years and proxy-reports from parents of pediatric subjects aged 2 to 18 years. The baseline is defined as the assessment collected during the subject's first study period, either at the visit of Cycle 1 Day 1 for the treatment period or the assessment at the visit of first 12-week interval for the no-treatment period, as appropriate. These analyses will not be presented for the Interim Analysis.

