Subjects who previously received teduglutide during TED-C13-003, as well as subjects who were in the standard of care treatment group, may be eligible to receive repeat doses of teduglutide 0.05 mg/kg subcutaneous (SC) once daily injection in this extension study. Subjects not receiving teduglutide treatment (i.e., in a no-teduglutide treatment [NTT] period), will be seen approximately every 12 weeks for safety, PS requirements, and quality of life. The first NTx visit following the screening visit should occur within 2 to 12 weeks of screening. At any point after screening or during a NTT period, subjects who meet at least one teduglutide treatment inclusion criteria, may proceed immediately to the pre-treatment visit if the investigator, subject, and parent agree to proceed with teduglutide therapy.

After the pre-treatment visit, subjects who meet at least one of the teduglutide treatment inclusion criteria, and meet none of the teduglutide treatment exclusion criteria, will start a 28-week cycle, consisting of 24 weeks of teduglutide treatment at 0.05 mg/kg SC once daily, followed by a 4-week follow-up period (during which no teduglutide is administered). During the 28-week cycle, clinic visits will occur at weeks 1, 2, 4, 6, 9, 12, 16, 20, 24, and 28. Phone visits are required approximately 1 week after adjustments in PS during the teduglutide treatment period (between weeks 1 and 24), and weekly during the teduglutide follow-up period (between weeks 24 and 28). Safety and PS requirements will be evaluated at every visit, and quality of life assessments will be made approximately every 12 weeks. If a subject has clinical deterioration and meets follow-up period escape criteria after stopping teduglutide, the subject may "escape" the follow-up period early and proceed immediately to another pre-treatment visit. Following completion of the 28-week treatment cycle, the subject will proceed to an NTT visit within approximately 12 weeks.

Document: \\quintiles.net\Enterprise\Apps\sasdata\SASa\sas\Shire\Teduglutide\ZXA48914\Biostatistics\Documentation\SAP\SHP633-303\_SAP\_Draft\_V1.0\_20171023

Author: [REDACTED]

Version Number:

Draft V1.2

Version Date:

16Jan2018

Template No: CS\_TP\_BS016 – Revision 3

Effective Date: 01May2012

Reference: CS\_WI\_BS005

Copyright © 2012 Quintiles Transnational Corp. All rights reserved.

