## 6. ANALYSIS SETS

Analysis of efficacy and safety endpoints will be performed based on the analysis sets defined in this section and as specified for each endpoint throughout this SAP.

Subjects will be classified in treatment groups based on whether they received teduglutide in the core study TED-C13-003 (as 0.0125 mg/kg/day, 0.025 mg/kg or 0.05 mg/kg) and/or during the prospective observation period in this study:

- TED/NTT – includes subjects who took teduglutide in the core study but not in the extension study;
- TED/TED – includes subjects who took teduglutide in the core study and in the extension study;
- ANY TED – includes subjects who took teduglutide in either the core study or in extension study.

No treatment-naïve patients in core study TED-C13-003 enrolled in the extension study SHP633-303, so the treatment groups associated with the NTT in the core study are removed from the statistical analysis.

---

Document: \\quintiles.net\Enterprise\Apps\sasdata\SASa\sas\Shire\Teduglutide\ZXA48914\Biostatistics\Documentation\SAP\SHP633-303\_SAP\_Draft\_V1.0\_20171023

Author: [REDACTED] Version Number: Draft V1.2  
Version Date: 16Jan2018

Template No: CS\_TP\_BS016 – Revision 3  
Effective Date: 01May2012

Reference: CS\_WI\_BS005

Copyright © 2012 Quintiles Transnational Corp. All rights reserved.  
The contents of this document are confidential and proprietary to Quintiles Transnational Corp. Unauthorized use, disclosure or reproduction is strictly prohibited.

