#### **17.5. ANALYSIS OF HRQOL VARIABLES**

Total scores, subscale scores and summary scores will be summarized by study visit and treatment group using descriptive statistics including number of subjects, mean, standard deviation, median, minimum and maximum. Change from baseline by visit will be summarized, with subjects excluded from change from baseline summaries at the visit associated with the subject's baseline measurement.

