Tables will present TED/NTT group first, followed by TED/TED. When required, a column for all subjects who exposed to teduglutide in core study or retrospective period in the extension study will be included and it will be labeled "ANY TED". The subjects will be grouped based on the treatment they received in the core study TED-C13-003 (teduglutide exposed and non-exposed) and prospective period (teduglutide exposed and non-exposed). For teduglutide treatment period tables, only TED/TED will be presented. If the number of treatment groups dictates that not all can fit on 1 page, then, unless specified in the corresponding "General considerations", it will be left to the discretion of the shell author, following discussions with study team, as to how these will be presented. For example, some of the treatment groups may be presented in a separate table. If the study is to be summarized by dose group rather than treatment group, then the nomenclature "Actual Dose" will be used in place of "Treatment Group" throughout. If presenting subgroups, TFL4Shire recommends that sub-headers are added so that a tabulation is repeated by subgroup (rather than adding extra columns in the table to show the subgroups). These should be ordered per the CRF decode e.g. 1=Male, 2=Female.

Document: \\quintiles.net\Enterprise\Apps\sasdata\SASa\sas\Shire\Teduglutide\ZXA48914\Biostatistics\Documentation\SAP\SHP633-303\_SAP\_Draft\_V1.0\_20171023

Author: [REDACTED]

Version Number:

Draft V1.2

Version Date:

16Jan2018

Template No: CS\_TP\_BS016 – Revision 3

Effective Date: 01May2012

Reference: CS\_WI\_BS005

Copyright © 2012 Quintiles Transnational Corp. All rights reserved.

The contents of this document are confidential and proprietary to Quintiles Transnational Corp. Unauthorized use, disclosure or reproduction is strictly prohibited.

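### HRQoL change in the Cycle 1 tables pools two baselines in the single TED/TED column, so it is change over the cycle for some subjects and change over the cycle plus an off-drug interval for others

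*SAP*

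**What the plan says.** All references are to the prospective SAP.

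- **Baseline.** Section 7.2 sets a core-study baseline unless otherwise specified. Section 17 specifies otherwise for HRQoL: "The baseline is defined as the assessment collected during the subject's first study period", that is, "either at the visit of Cycle 1 Day 1 for the treatment period or the assessment at the visit of first 12-week interval" of the no-treatment period. Nothing resets it when a subject later starts a cycle.
- **Two routes into Cycle 1.** Section 4.1: "At any point after screening or during a NTT period, subjects who meet at least one teduglutide treatment inclusion criteria" may move to the pre-treatment visit. A subject can therefore start Cycle 1 soon after screening or after time in NTT. On the NTT route, "The first NTx visit following the screening visit should occur within 2 to 12 weeks of screening".
- **One column.** Section 6 defines TED/TED without regard to starting period: it "includes subjects who took teduglutide in the core study and in the extension study". Appendix 1 adds: "For teduglutide treatment period tables, only TED/TED will be presented". Section 8.5 plans no subgroups and Section 8.1 no covariates.
- **Summaries.** Section 17.5: "Total scores, subscale scores and summary scores will be summarized by study visit and treatment group using descriptive statistics". Change from baseline is also summarized by visit, "with subjects excluded from change from baseline summaries at the visit associated with the" subject's own baseline measurement.
- **Assessments.** Section 17 schedules HRQoL at Day 1 and at two later points of each cycle. It labels these D12 and D24; I read them as Weeks 12 and 24, because Section 4.1 calls for quality-of-life assessments about every 12 weeks.

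**The concern.** A reader of a treatment-cycle table will take mean change at Cycle 1 Week 24 as the change that accompanied 24 weeks of treatment. Under this rule that holds for direct starters only. For an NTT-first subject, the same cell also holds whatever happened between the first NTT visit and Cycle 1 Day 1. That interval has no fixed length. It need not be neutral either, because entry to a cycle requires meeting at least one treatment criterion. The pooled mean then depends on how many subjects happened to start in NTT.

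The exclusion rule adds a second difficulty. Cycle 1 Day 1 is the baseline visit for direct starters, so they leave that change row and only NTT-first subjects remain. The Week 12 and Week 24 rows contain both groups. Reading down the column compares different subjects measured from different anchors.

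The whole analysis is descriptive (Sections 7.6 and 8.4), so the meaning of each cell is the result. What is at stake is whether these cells can be interpreted.

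**Working it through.** The plan states no HRQoL effect, variance or sample size by route, so there is no figure to reproduce. The check follows from the definitions.

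**Inputs from the SAP:** one baseline per subject, from the first extension period (Section 17); both routes open (Section 4.1); both routes in TED/TED (Section 6); TED/TED alone in cycle tables (Appendix 1); exclusion at the baseline visit (Section 17.5).

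**Inputs assumed, for illustration only:** T = +5 points, taken as equal on both routes; f = 0.25, 0.50, 0.75; D = −10, −5, 0, +5.

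**Step 1: change at Cycle 1 Week 24 by route.**
- Direct starter: Week 24 − Cycle 1 Day 1 = T.
- NTT-first: Week 24 − first NTT visit = (Cycle 1 Day 1 − first NTT visit) + (Week 24 − Cycle 1 Day 1) = D + T.

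**Step 2: pooled TED/TED mean.** (1 − f) × T + f × (T + D) = T + f × D.

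**Step 3: values with T = +5.**

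| f | D = −10 | D = −5 | D = 0 | D = +5 |
|---|---|---|---|---|
| 0.25 | 2.5 | 3.75 | 5.0 | 6.25 |
| 0.50 | 0.0 | 2.5 | 5.0 | 7.5 |
| 0.75 | −2.5 | 1.25 | 5.0 | 8.75 |

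The shift f × D runs from 0.75 × (−10) = −7.5 to 0.75 × 5 = +3.75 points. Measured from Cycle 1 Day 1 in everyone, each cell would be +5.0. The planned value agrees only when D = 0 (or f = 0).

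**Step 4: the Cycle 1 Day 1 change row.** It holds f × N subjects, against N in later rows. With an assumed N = 40 in the column and f = 0.50, that is 20 at Day 1 and 40 at Weeks 12 and 24, when data are complete.

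**Step 5: what a reader could recover.** With complete data the Day 1 row estimates D, and its n over the later n estimates f. For f = 0.50 and D = −10: pooled 0.0 − 0.50 × (−10) = +5.0, which is T. The mean actual scores at Day 1 and Week 24 also differ by T. Neither route returns the SD or median of within-cycle change. The planned SD also contains a between-route part: f × (1 − f) × D² = 0.5 × 0.5 × 100 = 25 on the variance scale in this example. With missing questionnaires, the rows no longer describe the same subjects and the subtraction is only approximate.

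**The case against.** The strongest reply is that the rule is coherent. It applies one definition to everyone, change since the first HRQoL assessment of the first extension period. It parallels the reference start date in Section 7.1 and suits the long-term objective in Section 3.2. Excluding subjects at their own baseline visit is also correct, since their change there is zero by construction. The planned actual-score rows show the movement from Day 1 to Week 24. All of this stands, and it limits the point: change since entry to the extension is a legitimate summary and should be kept. It does not supply a change cell with one meaning in a table organized by cycle visit.

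The phrase that ends the baseline definition, leaving the choice as appropriate, could be read as a separate baseline for each type of period. The reference to the subject's first study period, and to the subject's own baseline measurement in Section 17.5, make that the weaker reading. If it is intended, the text should say so.

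Two stronger inferences are tempting, and the SAP does not support them. A reader might infer that on-drug and off-drug baselines are mixed. They are not: both anchors precede dosing in the extension, and all TED/TED subjects had teduglutide in the core study, so Cycle 1 Day 1 is not first exposure. A reader might also infer that the parenteral support tables avoid the difficulty. Their anchor is the same for everyone, but change there also spans the off-drug interval for NTT-first subjects. The distinctive feature of HRQoL is that the anchor itself differs between subjects within one column.

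**Conclusion.** The point holds as a matter of interpretation. As written, mean HRQoL change at Cycle 1 Week 12 and Week 24 in the TED/TED column estimates T + f × D, and the Cycle 1 Day 1 change row describes NTT-first subjects only. Mean, SD and median in those cells cannot be read cleanly as change over the cycle or as change over a common period.

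The size is unknown because the SAP gives neither f nor D. The range of −2.5 to +8.75 around a within-cycle change of +5 rests entirely on assumed inputs and on equal T in both routes. A reader might infer that the rule hides benefit. That requires D to be negative; a positive D would flatter the change, and D = 0 would leave it untouched.

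HRQoL is outside the interim analysis (Section 17) and no hypothesis is tested, so no error rate or formal conclusion is affected. The planned actual-score summaries partly reveal the within-cycle movement.

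**What to change.** 1. In the treatment-cycle HRQoL tables, add change from Cycle x Day 1 to Cycle x Week 12 and Week 24 for every subject with both assessments.
2. Keep change since the first extension assessment as a separately labelled long-term summary, shown by starting period (direct to cycle, or NTT first).
3. State in Section 17 that the first-assessment baseline is one per subject, and say which baseline applies to a subject who leaves NTT before the first NTT visit.

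Cost: wording in Sections 17 and 17.5, a second baseline flag and additions to the shells. Cycle x Day 1 is already a scheduled assessment, so no new data are needed. The plan is a draft (V1.2), and HRQoL is not due until the final analysis.

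Two downsides should be stated in the SAP. Subjects without a Cycle x Day 1 questionnaire drop out of that cycle's change. And because entry to a cycle depends on treatment criteria, Day 1 may be a selected low point, so within-cycle change may include regression to the mean. For example, assumed scores of 70 at the first NTT visit, 60 at Cycle 1 Day 1 and 70 at Week 24 give 70 − 60 = +10 within the cycle but 70 − 70 = 0 since the first assessment. This is why the within-cycle change should be added beside the long-term change, not put in its place.
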